#### Change from baseline to Week 24 in NC symptom severity score:

On a daily basis from Visit 1 and throughout the study, the participant will use a diary to respond to the morning individual rhinosinusitis symptom questions evaluating symptom severity over the past 24 hours using a 0 to 3 categorical scale (where 0 = no symptoms, 1 = mild symptoms, 2 = moderate symptoms, and 3 = severe symptoms) as described in Table 6 below.

**Table 6 - Symptom severity score**

Scale	Symptom severity description
0	No symptoms
1	Mild symptoms (symptoms clearly present, but minimal awareness and easily tolerated)
2	Moderate symptoms (definite awareness of symptoms that is bothersome but tolerable)
3	Severe symptoms (symptoms that are hard to tolerate, cause interference with activities or daily living)

A NC symptom severity score  $\geq 2$  at Visit 1 and a weekly average severity  $> 1$  at the time of enrollment (Visit 2) are required and will be provided to the site to determine participant eligibility. The participant must have 4 or more measurements collected within 7 days prior to enrollment; the baseline will be the average of the non-missing measurements.

For the baseline to EOT/EOS analysis, the average of the symptom severity scores from the most recent 4 weeks before a scheduled visit will be used.

#### Change from baseline to Week 24 in LMK score

Computerized tomography (CT) scan should be performed anytime during the Screening Period before the first administration of IMP and at Visits 7 and 9 (Weeks 24 and 52). Whenever possible, a cone beam CT scan should be utilized.

Details for CT are available in a separate operational manual provided to the sites.

The LMK system is based on localization with points given for degree of opacification: 0 = normal, 1 = partial opacification, 2 = total opacification. These points are then applied to the maxillary, anterior ethmoid, posterior ethmoid, sphenoid, and frontal sinus on each side. The osteomeatal complex (OC) is graded as 0 = not occluded or 2 = occluded. Adding the scores of these 6 parameters will derive a maximum score of 12 per side (left and right). The total score of the 2 sides will be used for analysis. This scoring system has been validated in several studies(1)(2)(3).

For participants in whom the OC is missing (because of a previous surgery), the reader should consider the location of the previous OC and provide a score (as if the OC were there).

#### **4.4.1.2 Main analytical approach**

##### Handling of missing data

Each of the 3 key secondary efficacy endpoints will be analyzed using the PP population and a hybrid method of worst observation carried forward (WOCF) and multiple imputation. For participants taking rescue medications or who undergo surgery, their data after the medication usage or surgery will be set to missing, and the worst postbaseline value on or before the time of the medication usage or surgery will be used to impute the missing Week 24 value. Participants who discontinue the treatment prematurely are encouraged to follow the planned clinical visits, and in those participants who did not take rescue medications or undergo surgery, all data collected after treatment discontinuation will be used in the analysis. For these participants, missing data may still happen despite all efforts to collect the data after treatment discontinuation. For participants who discontinue due to lack of efficacy, all data collected after discontinuation will be used in the analysis, and a WOCF approach will be used to impute the missing Week 24 value if needed. For participants who discontinue not due to lack of efficacy, a multiple imputation approach assuming missing at random will be used to impute the missing Week 24 value, and this multiple imputation will use all participants, excluding participants who have taken rescue medications or undergone surgery on or before Week 24 and excluding participants who discontinue due to lack of efficacy on or before Week 24. All of the imputed complete data will be analyzed by descriptive statistics with the 95% CI. The summarized mean changes obtained from each imputed dataset will be combined using Rubin's rule for a single estimate.

The following steps will be used to create the primary imputed datasets:

- Impute any missing baseline values with the mean baseline value of all participants with non-missing baseline data.
- For participants who are rescued (undergo surgery for NP or receive SCS for any reason) or discontinue treatment early due to lack of efficacy:
  - Set all data on or after earliest date of rescue or treatment discontinuation to missing.
  - Replace all missing values with the worst observation prior to the missing data through Week 24, including baseline values.
- For participants who are not rescued, discontinue treatment for reasons other than lack of efficacy, or complete the study:

- Create 1 dataset with monotone missing pattern using the Markov Chain Monte Carlo (MCMC) method including values at all applicable visits through Week 24 in chronological order including baseline.
- For participants having missing data at Week 24 regardless of reason(s), a multiple imputation (MI) approach will be used to impute the missing endpoint value
- Set both datasets together.
- The remaining missing data will be imputed 40 times using the regression method for the monotone pattern with adjustment for values at all applicable visits through Week 24 in chronological order including baseline.
- Applying Rubin's rule to combine analysis results (means and standard errors) from 40 imputations using PROC MIANALYZE for the final estimated mean and 95% CL.

Missing data related to the key secondary endpoints will be tabulated including by relation to the COVID-19 pandemic. If necessary, additional supplementary analyses will be presented.

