6.8.1 Rescue medicine and procedures

During the study intervention period, based on clinical evaluation, in case of worsening of signs and/or symptoms requiring medical intervention, the following rescue medications/procedures may be employed as per Investigator's judgment:

1. Systemic (eg, oral) corticosteroids up to 2 weeks
2. Antibiotics for the treatment of acute sinusitis less than 2 weeks after Visit 2
3. Sinonasal surgery

Participants receiving rescue treatment other than surgery during the study should continue on IMP unless the Investigator decides to withdraw the study intervention. Before starting treatment with SCS, participants should come to the study site for the clinical assessments including endoscopy.

For participants who undergo or plan to have surgery for NP, the Investigator may decide to continue IMP up to the time of surgery or EOT, whichever date comes first. At the time of surgery, participants will be permanently discontinued from study intervention and assessed as soon as possible using the procedures normally planned for the EOT/EOS Visit as described in the SoA ([Section 1.3](#)).

If the surgery is to be performed during the intervention period, an AE or SAE page will be completed. If surgery is scheduled after the planned EOS, the EOT/EOS Visit will not be delayed. The surgery will be followed up by the Investigator or the participant's physician with general medical practice.

In any case, participants who prematurely discontinue the treatment will be encouraged to return to the study site for the efficacy and safety assessments planned at the EOT/EOS Visit (refer to SoA [[Section 1.3](#)]).

The date and time of rescue medication administration as well as the name and dosage regimen of the rescue medication must be recorded. For participants who undergo sinonasal surgery for NP, the reason (worsening signs and/or symptoms during the study), the expected and real surgery

dates, and the type and outcome of surgery will be recorded. For participants who plan to have sinonasal surgery for NP, the reason (worsening signs and/or symptoms during the study), the expected and real surgery dates, and the type of surgery will also be recorded in the e-CRF.

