Key secondary endpoints	Change from baseline to Week 24: 
 
• Bilateral NPS
 
• NC symptom severity score
 
• LMK score
 
	PP	The intercurrent events will be handled as follows: 
 
• Taking rescue medications or undergo surgery prior to Week 24: data will be set to missing after the medication usage, and the participant's worst postbaseline value on or before the time of the medication usage or surgery will be used to impute the missing Week 24 value (for participants whose postbaseline values are all missing, the baseline will be used to impute) (hypothetical strategy)
 
• Discontinuing the treatment prematurely (Participants who did not take rescue medications or undergo surgery): all data collected after treatment discontinuation will be used in the analysis (treatment policy strategy).
 
	All imputed, complete data will be analyzed by descriptive statistics and 95% CI. The summarized mean changes obtained from each imputed dataset will be combined using Rubin's rule for a single estimate.

Estimands				
Endpoint Category	Endpoint	Population	Intercurrent event(s) handling strategy (The missing data handling)	Population-level summary (Analysis method)
Other secondary efficacy endpoints	
 
• Change from baseline to Week 24:
 
• Total symptom score
 
• Loss of smell symptom severity score
 
 Visual analogue scale for rhinosinusitis		In addition, the missing data imputation rules are as follows: 
 
• After treatment discontinuation due to lack of efficacy prior to Week 24: WOCF approach will be used to impute the missing Week 24 value if needed
 
• After treatment discontinuation due to reasons other than lack of efficacy prior to Week 24: multiple imputation approach assuming missing at random will be used to impute the missing Week 24 value, and this multiple imputation will use all participants, excluding participants who have taken rescue medications or undergone surgery on or before Week 24 and excluding participants who discontinue due to lack of efficacy on or before Week 24.
 
	

Estimands				
Endpoint Category	Endpoint	Population	Intercurrent event(s) handling strategy (The missing data handling)	Population-level summary (Analysis method)

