##### **4.4.2.1 Definition of endpoints**

###### Change from baseline at Week 24 in TSS and Loss of smell severity score

TSS is a composite score (ranging between 0 and 9) consisting of the sum of the following symptoms assessed daily in the morning: nasal congestion/obstruction, decreased/loss of sense of smell, and rhinorrhea (average of the non-missing anterior/posterior nasal discharge). At least 2 symptoms scores must be reported to calculate the TSS, otherwise the score will remain missing.

The symptoms scores at baseline and changes from baseline will be calculated using the same approach as for NC as described in Section 4.4.1.1. Baseline is defined as the average of the non-missing 7 days prior to enrollment and requires  $\geq 4$  responses. Timepoints will be evaluated using the average symptom severity from the most recent 28 days before each scheduled visit. Participants with fewer than 28 days in between visits will use data from one day after the previous visit through the day of the current visit. At least 50% of days (with a maximum of 28) must be non-missing in order to calculate the average symptom severity.

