## 5.4.5 Timepoint assessment

### Analysis windows for time points

For VAS for rhinosinusitis, Vital signs, and Laboratory assessments. The analysis windows post baseline of [Table 10](#) will be generated.

A measurement (scheduled or unscheduled) will be used if it is available and measurement date is within the analysis window.

After applying these time windows, if multiple assessments are associated to the same time point, the closest from the targeted study day will be used. If the difference is a tie, the value after the targeted study day will be used. If multiple valid values exist within a same day, then the first value of the day will be selected.

If there is no measurement for a given parameter in an analysis window, data will be considered missing for the corresponding visit.

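### SAP 4.4.1.2 gives conflicting rules on which values feed the worst-observation imputation for rescued participants, so the pre-rescue state can be lost

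*SAP*

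**What the plan says.** SAP 4.4.1.2 handles rescued participants (surgery, or SCS for any reason) by worst observation carried forward (WOCF). Its narrative says that "the worst postbaseline value on or before the time of the medication usage or surgery will be used to impute" the missing Week 24 value. Table 3, like Protocol 9.3.3, adds a fallback: "for participants whose postbaseline values are all missing, the baseline will be used to impute".

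The programming steps later in 4.4.1.2 read differently. First: "Set all data on or after earliest date of rescue or treatment discontinuation to missing". Then: "Replace all missing values with the worst observation prior to the missing data through Week 24, including baseline values".

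Three other provisions decide which values are available:

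- Protocol 6.8.1: "Before starting treatment with SCS, participants should come to the study site for the clinical assessments including endoscopy".
- SAP 5.4.5: "A measurement (scheduled or unscheduled) will be used if it is available and measurement date is within the analysis window", but "if multiple assessments are associated to the same time point, the closest from the targeted study day will be used".
- SAP 4.4.2.1, for TSS and smell, which follow the nasal congestion (NC) approach: "Timepoints will be evaluated using the average symptom severity from the most recent 28 days before each scheduled visit". At least half of the days must be completed.

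**The concern.** WOCF is meant to carry a rescued participant's worst state up to rescue. The text does not settle which values compete for worst, whether a value from the rescue day counts, or whether baseline competes. Two programmers could follow this SAP and produce different Week 24 values for the same participant.

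The direction is one-sided. Higher scores are worse, and removing candidates from a maximum can only lower it, so any loss makes the mean change look better or leaves it alone. The changes in NPS and NC are among the measures meant to show efficacy similar to EFC14280 (Protocol 4.2.2). No hypothesis is tested (SAP 4.6), so the point estimates carry the message.

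**Working it through.** **Plan's own figure.** SAP 2 states 20 participants, a 62% responder rate, at least 50% observed, 90% probability. P(X ≥ 10 | n = 20, p = 0.62) = 0.908, and 20/(1 − 0.20) = 25. Both reproduce. This point does not rest on them; n = 20 is used only for scale.

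**1. The two rules side by side**

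| | Narrative with Table 3 | Programming steps |
|---|---|---|
| Value dated on the rescue day | Kept | Removed |
| Baseline | Only if no postbaseline value exists | Always a candidate |
| Best possible imputed change | Can be an improvement | 0 |

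SAP 5.2, which lists changes from the protocol, does not mention the different role of baseline.

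**2. Endoscopy, if WOCF runs on visit-level data.** Table 10 windows and target days: Week 4, up to Day 42 (29); Week 8, Days 43–84 (57); Week 16, Days 85–140 (113); Week 24, Days 141–224 (169). Assumptions: visits on target, pre-SCS endoscopy the day before SCS, SCS starting on any of Days 3–168 (166 days).

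- The endoscopy always falls inside a window.
- Post-rescue data removed first, then closest to target chosen: the pre-SCS endoscopy loses whenever that window's scheduled one is already done. Days 30–42 (13) + 58–84 (27) + 114–140 (27) = 67; 67/166 = 40%.
- Windows applied first: it survives for 3 of 166 days.
- All pre-rescue values used: never lost under these assumptions. An endoscopy on the SCS start day itself is always lost under the programming steps.

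**3. Diary scores.** With visits on target and averages ending on the visit day, the means use Days 2–15, 16–29, 30–57, 86–113 and 142–169. Days 58–85 (28) and 114–141 (28) enter none: 56 of 168 days, 33%.

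Invented example: NC is 2.0 to Day 14, 1.5 to Day 29, 1.0 to Day 127, then 3.0 until SCS on Day 155.

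- Week 2 mean: (13 × 2.0 + 1.5)/14 = 1.96. This is the worst visit value; Weeks 4, 8 and 16 give 1.5, 1.0 and 1.0.
- Week 24 window: Days 142–154 give 13 of 28 days, below half, so no value.
- Last 28 days before rescue (127–154): (1.0 + 27 × 3.0)/28 = 2.93.

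**4. Effect on the imputed NPS change.** Invented values: baseline 6; Weeks 4 and 8 both 5; pre-SCS endoscopy on Day 80.

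| Rule and data | Pre-SCS score 6 | Pre-SCS score 7 |
|---|---|---|
| Narrative, visit-level | 5 − 6 = −1 | −1 |
| Narrative, all values | 6 − 6 = 0 | 7 − 6 = +1 |
| Steps, visit-level | 6 − 6 = 0 | 0 |
| Steps, all values | 0 | +1 |

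**5. Effect on the mean.** Shift = (number rescued × points lost)/n. With n = 20, one rescued participant gives 1/20 = 0.05 per point and five give 0.25. For the NC example under the steps, the loss depends on baseline: 2.93 − 2.0 = 0.93 (0.93/20, about 0.05); 2.93 − 2.5 = 0.43 (about 0.02); nil at 3.0.

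**The case against.** The strongest defence is that the SAP nowhere says the worst value comes from windowed data. A reader might infer that it does, and that unscheduled endoscopies have no role. The documents do not support either as a stated rule. The quoted sentence carries no such restriction, and SAP 5.4.5 admits unscheduled measurements into the windows. Its lead-in does not even name endoscopy, although Table 10 has a column for it. This part stands: the visit-level source is an inference. It is nevertheless the natural one. The steps stack the rescued participants with a dataset built from values at the applicable visits, and diary scores are defined only as means before scheduled visits.

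A reader might also infer that rescued participants are routinely credited with an early response. The steps block that: with baseline a candidate, the imputed change cannot be an improvement. Credit is possible only under the narrative and Table 3 rule.

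Three further limits stand:

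- It is not true that worsening after Day 113 never reaches a diary mean. If data are removed day by day, SCS on Day 156 or later leaves at least 14 of the 28 Week 24 days, which meets the 50% rule. On that reading at least one of the seven days before rescue enters a mean for 83 of 160 SCS start days (Days 9–168, 52%). If data are removed by visit, it is 28 of 160 (18%).
- The 40% and 33% are shares of calendar days, not of rescues or of bias.
- Rescue includes SCS for any reason, so not every rescued participant is a treatment failure for polyps.

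None of this removes the contradictions over the rescue day and over baseline. Those are in the text itself.

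**Conclusion.** SAP 4.4.1.2 conflicts with itself on values dated on the rescue day, and its steps conflict with Table 3 on baseline. If WOCF is run on visit-level data, the pre-SCS endoscopy and parts of the diary can also drop out. For NPS, NC, TSS and smell the effect is favourable or nil, at about 0.05 on a 20-participant mean per point lost per rescued participant. Under the steps only worsening beyond baseline is lost; under the narrative an improvement could be credited.

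The primary endpoint is unaffected, because rescued participants are nonresponders after rescue (SAP 4.3.2). A reader might extend the point to all three key secondary endpoints, but no CT is planned between screening and Week 24, so the Lund Mackay score carries baseline under either rule.

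The total size is unknown, because the documents give no rescue rate. The day counts assume visits on target and complete diaries. The 50% rule is written for TSS and smell, and applying it to NC is an assumption.

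**What to change.** In SAP 4.4.1.2 and Table 3:

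- State that the worst value for WOCF is taken over all centrally read endoscopies, scheduled or unscheduled, up to and including the pre-rescue assessment (same day included), before the Table 10 selection of one value per window. Align the step that removes data with this.
- For NC, TSS and smell, add as a candidate the mean of the last 28 days before rescue, with at least 50% of days completed. This is one reasonable convention; the documents do not dictate it.
- State one rule on whether baseline is a candidate, and use it in the narrative, the steps and Table 3. If it departs from Protocol 9.3.3, list it in SAP 5.2.

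The cost is SAP wording and a little programming on assessments that the protocol already schedules or calls for. The mean changes may come out slightly less favourable.

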9.1 SAMPLE SIZE DETERMINATION

In EFC14280, the proportion of responders (NPS improvement from baseline ≥ 1) at Week 24 was 62.0% in the dupilumab group. Based on this result, the proportion of responders (NPS improvement from baseline ≥ 1) at Week 24 in this postmarketing study will be at least 50.0% to justify the similar effect size between EFC14280 and this study.

It is necessary for 20 participants to achieve this similar responder rate (at least 50%) with a 90% probability of success. The sample size was adjusted up to 25 to account for a 20% drop-out rate.

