### 4.3.2 Main analytical approach

The number of participants and percentage with the 95% continuity corrected Wilson confidence interval (CI) will be provided at Week 24 using the PP population.

The main strategy for handling intercurrent events will be a Composite approach, where participants who are rescued (undergo surgery for NP or receive SCS for any reason) will be considered nonresponders for time points after rescue. Participants who have missing data at Week 24 will be considered nonresponders.

The date of rescue will be the earliest date of any intercurrent events that occur.

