## **4.6 MULTIPLICITY ISSUES**

No hypothesis testing will be performed within this study.

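### Key secondary mean changes: Week 24 values still missing after a stop for reasons other than lack of efficacy are imputed as if treatment had continued, most clearly for LMK, and no planned analysis tests this

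*SAP*

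**What the plan says.** For the key and other secondary endpoints in the PP population, SAP Table 3 handles premature discontinuation without rescue or surgery as follows: "all data collected after treatment discontinuation will be used in the analysis (treatment policy strategy". Missing-data rules are listed separately in the same cell. After a stop for lack of efficacy, a missing Week 24 value is replaced by the worst observation carried forward (WOCF). After any other stop, "a multiple imputation approach assuming missing at random will be used to impute the missing Week 24 value". Participants who were rescued, operated on or stopped for lack of efficacy are left out of the imputation model. Protocol 9.3.3 has the same rule.

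The step list in SAP 4.4.1.2 puts the other stops in one group with completers. It imputes 40 times by regression on baseline and the values at the applicable visits through Week 24. No covariate marks treatment status or time since stopping.

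The supplementary analysis (Table 3, mITT row, and SAP 4.4.1.3) changes the population but keeps this rule. SAP 4.4.1.2 adds only that further supplementary analyses will be presented if necessary, and SAP 4.8 plans no other analyses.

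For the primary endpoint the rule is different: "Participants who have missing data at Week 24 will be considered nonresponders" (SAP 4.3.2).

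**The concern.** A treatment-policy mean needs the Week 24 outcome whether or not the drug was continued. Where that outcome is observed after a stop, the plan uses it, and there is no difficulty. Where it is not observed, the model predicts it mainly from people still on dupilumab. If some of the effect is lost after stopping, the prediction is too favourable.

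Protocol 3.1 and 4.2.2 say these means are to be evaluated to show efficacy similar to that of dupilumab with INCS in EFC14280. In a single-arm study, an optimistic imputation moves the reported mean directly. A reader would not learn from the planned output how far the mean depends on this assumption.

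**Working it through.** **1. The plan's own figures.** Protocol 9.1 reports that the EFC14280 responder rate "at Week 24 was 62.0% in the dupilumab group", and continues: "It is necessary for 20 participants to achieve this similar responder rate (at least 50%) with a 90% probability of success". Exact binomial: P(X ≥ 10 | n = 20, p = 0.62) = 0.908, so the stated 90% is reproduced. Then "The sample size was adjusted up to 25 to account for a 20% drop-out rate": 20 / (1 - 0.20) = 25, also reproduced. At that drop-out the model would hold about 20 on-treatment participants against at most 5 stopped ones, so the pool is mostly on treatment.

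**2. Which values are affected.** Only Week 24 values that are missing after a stop for a reason other than lack of efficacy.
- NPS: Protocol 7.1.1 has stopped participants assessed as soon as possible with the EOT/EOS procedures. The Week 24 endoscopy window in SAP Table 10 is Days 141 to 224. An earlier endoscopy is assigned to an earlier visit, and Week 24 stays missing unless the participant returns. The earlier value still enters the regression.
- LMK: Protocol 7.1.1 excludes the CT scan from the assessments after a permanent stop, and CT is scheduled only at screening, Week 24 and Week 52 (SAP 4.4.1.1). The model then has only baseline to work with.

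**3. Size.** The documents give no mean change, SD or off-treatment value, so this is a range. Let D be the on-treatment mean change, m of N values imputed, s = m/N, and r the fraction of D kept at Week 24 after stopping. Assume stopped participants would on average have reached D had they continued.
- Mean under the plan ≈ D.
- Treatment-policy mean = D[1 - s(1 - r)].
- Shift = |D| × s × (1 - r).

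With D = -2.0 on the NPS (assumed) and N = 25:

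| Imputed (m) | Mean, r = 0 | Shift | Mean, r = 0.5 | Shift | Shift, r = 1 |
|---|---|---|---|---|---|
| 2 | 23 × (-2.0)/25 = -1.84 | 0.16 | (-46 - 2)/25 = -1.92 | 0.08 | 0 |
| 3 | 22 × (-2.0)/25 = -1.76 | 0.24 | (-44 - 3)/25 = -1.88 | 0.12 | 0 |
| 5 | 20 × (-2.0)/25 = -1.60 | 0.40 | (-40 - 5)/25 = -1.80 | 0.20 | 0 |

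Relative to the treatment-policy mean, five imputed values overstate the change by 2.0/1.6 - 1 = 25% (r = 0) or 2.0/1.8 - 1 = 11% (r = 0.5).

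**4. Check by simulation.** Regression imputation was simulated with N = 25, 5 stopped and unobserved afterwards, visits at Weeks 0, 4, 8, 16 and 24, and assumed D = -2, SD 1.5 and adjacent-visit correlation 0.75. The imputed-data mean stayed between -1.98 and -2.02. The treatment-policy mean was about -1.6 (r = 0) or -1.8 (r = 0.5). Whether the last visit before stopping was Week 4, 8 or 16 made no material difference, and neither did having intermediate visits (as for NPS) or baseline only (as for LMK). In this set-up stopping was unrelated to earlier response and no post-stop visit was observed. The softening from such values, available for NPS and NC, is therefore not in these figures.

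**The case against.** - **Table 3 is not self-contradictory.** It lists treatment policy as the intercurrent-event strategy and missing at random (MAR) as a separate missing-data rule. A reader might infer that the plan has silently adopted a second, hypothetical strategy; the layout does not support that. What stands is that, without off-treatment information, the MAR assumption does not deliver the labelled target for the missing part.
- **NPS and NC imputation uses the participant's own record.** A reader might infer that everyone who stopped simply receives the completers' improvement. The regression conditions on earlier visits and any observed post-stop visits, and non-efficacy stops with Week 24 data stay in the pool. The reading comes close only for LMK.
- **Five of 25 is not the plan's forecast.** The 20% drop-out covers all causes. Some of those participants may be rescued, operated on or stopped for lack of efficacy (all WOCF), be excluded from PP for INCS use, or return for Week 24.
- **The stated similarity criterion is the responder rate** (Protocol 9 and 9.1), where a missing value already counts as nonresponse, and "No hypothesis testing will be performed within this study". A reader might infer that the similarity conclusion itself is biased. The documents do not show that. They also do not say how EFC14280 imputed its dupilumab arm; with the same method, the optimism would lie on both sides.
- **Some information is already planned.** Missing key secondary data are tabulated, and SAP 4.5.2.3 gives by-visit summaries without imputation. These show how many values are imputed, but they do not test the assumption.

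**Conclusion.** The concern holds in a limited form. For the key secondary mean changes, the imputed part of the estimate approximates continued treatment, and no planned analysis shows how much that matters. It is strongest for LMK and weaker for NPS and NC. The main primary analysis is unaffected.

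The size cannot be fixed from the documents. It depends on how many values are missing after such stops and how much effect is lost. Under the assumed -2.0, it runs from zero through 0.08 to 0.24 NPS points (2 or 3 missing) to 0.2 to 0.4 points (5 missing, the upper bound). The case for acting is that the means are meant to support similarity with EFC14280 and the check is cheap. It is not that the main analysis is wrong.

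**What to change.** 1. Keep the main analysis. It follows Protocol 9.3.3, and SAP Appendix 2 already seeks consistency with EFC14280 in rescue handling.
2. Add to SAP 4.4.1.3 one sensitivity analysis for each key secondary endpoint. Retain all observed post-stop data. Where Week 24 is still missing after any treatment stop, use the worst observed value, baseline included. Each replaced change is then zero or a worsening, so report the result as a conservative bound, not as a treatment-policy estimate.
3. Add to Table 3 that treatment policy is realised where post-stop data exist, and that the missing part rests on an MAR, on-treatment-like assumption. Align the mITT row, which labels the same handling a composite policy, with SAP 4.4.1.3, which calls it treatment policy.
4. Before reusing the WOCF code, reconcile SAP 4.4.1.2 with itself. For lack-of-efficacy stops the prose uses post-stop data, while the step list sets them to missing. Run unchanged for all stops, those steps would delete data that the plan says it keeps.
5. Reconcile the CT passages. Protocol 7.1.1 excludes CT after a permanent stop but also refers to the EOT/EOS procedures, and the Week 24 CT window in SAP Table 10 opens right after the first dose.

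Cost: SAP wording and one rerun of adapted code. The downside is a second, less favourable figure in the report.
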